#### 13.3.1. Analysis Populations

The analysis populations are defined below.

# 13.3.1.1. Full Analysis Set

The Full Analysis Set (FAS) population will include all subjects/subject attacks treated. Subjects/subject attacks will be analyzed according to the treatment randomized. The FAS population will be the primary population for efficacy analyses.

## 13.3.1.2. Safety Population

The safety population will include all subjects who received at least 1 dose of study drug. Subjects will be analyzed according to the treatment received. This population will be used for all analyses of accountability, demographics, and safety.

## 13.3.2. Subject Demographic and Disposition Data

Demographic data and baseline characteristics including age, gender, race or ethnicity, height at screening, weight at screening, and BMI at screening will be summarized by treatment sequence using descriptive statistics.

Disease and treatment characteristics including years since initial diagnosis of HAE, number of days since last HAE attack, documented attack frequency, and pattern of on-demand therapy will be summarized by treatment sequence using descriptive statistics.

Subject disposition will be presented for all subjects. The number of subjects who completed the study and discontinued from the study will be provided. The reasons for early discontinuation also will be presented. A tabulation of the number of subjects exposed to study drug will be presented.

# 13.3.3. Analysis of Efficacy Variables

As this is the first study of BCX7353 in the treatment of acute attacks, the analysis of attack resolution will be described in a number of ways which will be fully detailed in the SAP. The endpoint that may be utilized to first examine efficacy is the proportion of subject attacks with a stable or improved VAS at 4 hours postdose in the full analysis set. The number and proportion of subject attacks with a stable or improved VAS at 4 hours postdose will be summarized by treatment group. Attacks that require standard of care medication prior to the 4 hour time point will be considered as failure (i.e., not having a stable or improved VAS at 4 hours postdose). To assess treatment differences, a logistic mixed effect model including treatment, period and sequence as fixed effects, and subject within sequence as a random effect will be utilized. Other binary endpoints will be analyzed in a similar manner.

The 3-symptom composite VAS and its associated changes from baseline will be summarized for each attack by time point and treatment group. Treatment differences in the change from baseline values at each time point will be assessed with a mixed effect linear model with factors for treatment, period, sequence, and baseline value as fixed effects, and subject within sequence as a random effect. Analyses of other continuous variables will be analyzed in a similar manner.

The time to use of standard of care medication will be estimated using the method of Kaplan-Meier. For each attack, subjects who do not use standard of care medication will be censored at the end of the attack observation period (i.e., 24 hours). Treatment differences will be assessed using an appropriate proportional hazards model. Analyses of other type to event variables will be analyzed in a similar manner.

Location of attacks, duration of attacks, and number of acute HAE medications administered will be summarized for each treatment group.

## 13.3.4. Analysis of Safety Variables

Adverse events will be mapped to a Medical Dictionary for Regulatory Activities (MedDRA) preferred term and system organ classification. Any event reported on the subject's study record that occurs on or after the initiation of study drug within a given treatment period is defined as treatment emergent. Additionally, it is assumed that an AE that is reported to have started on the day of subject dosing to treat an attack without an associated onset time may have occurred after the initiation of study drug. Hence, AEs occurring on the day of subject dosing to treat an attack with no associated onset time will be assumed to be treatment emergent. AEs will be attributed to the corresponding treatment assignment of the corresponding treatment period. The occurrence of treatment-emergent AEs will be summarized by treatment group using MedDRA preferred terms, system organ classifications, and severity. Separate summaries of treatment-

emergent SAEs and AEs considered to be related to study drug will be generated. All AEs will be listed for individual subjects showing both verbatim and preferred terms.

Descriptive summaries of vital signs, weight, ECG parameters, and clinical laboratory results will be presented separately for each treatment group. Laboratory abnormalities will be graded according to the DMID Adult Toxicity Table (Publish Date: Draft, November 2007, see Appendix 15.1). Any graded abnormality that occurs following the initiation of study drug and represents at least 1-grade increase from the baseline assessment for a given treatment period is defined as treatment emergent. The number and percentage of subjects experiencing treatment-emergent graded toxicities will be summarized by treatment group. Laboratory toxicity shifts from baseline to post-baseline assessments will be summarized by treatment group.

Clinically significant abnormal morphological ECG findings will be summarized by treatment group.

Physical examination results will be presented in listings.

Concomitant medications will be coded using the World Health Organization (WHO) dictionary. These data will be summarized by treatment group.

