## Presumed Phospholipidosis (PLD):

In the 28 day studies in both rats and monkeys, foamy macrophages and vacuolated infiltrates were found in multiple organs and various tissues, and presumed to be signs of PLD. PLD can only be confirmed with electron microscopy which was not done in the 28 day study. In most tissues, these infiltrates did not appear to be adverse and there were no clinical or blood chemistry findings that correlated. Importantly, the infiltrates were fully or partially reversible in both species. The partial reversibility in monkeys may have been due to the continued presence of BCX7353 in plasma even at Day 50 of the 28-day dosing study.

In the 13-week studies in rats, the liver showed vacuolated macrophages with electron microscopic features consistent with PLD. In the monkey 13-week study there were no microscopic abnormalities, and no foamy macrophages or vacuolated cellular infiltrates were observed. Increased urinary levels of di-docosahexaenoyl (22:6)-Bis(mono)acylglycerol phosphate (BMP), an investigational biomarker for PLD, were demonstrated in both rats and monkeys dosed with BCX7353 for 13 weeks. This increase was dose related and reversible upon cessation of BCX7353 in both species. These data suggest that the urinary BMP changes induced by BCX7353 in both rats and monkeys may not be associated with PLD, given the differences seen microscopically between the two species.

PLD is not adverse in and of itself and there are many approved products that cause this phenomenon without any unmanageable toxicities. Since PLD requires accumulation of drug, it is highly unlikely that subjects are at any risk of this phenomenon with individual doses of study drug, separated by at least 14 days at a minimum. The primary method of ensuring subject safety will be to monitor organ toxicity and subject well-being through adverse event reporting and vital signs including weight. Since phospholipidosis is not toxic in and of itself, organ health including function and signs of inflammation will be monitored. Monitoring of renal, liver, cardiac, and muscle health will be achieved with routine safety assessments, including ECGs.

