#### 10.2. Schedule of Assessments

The schedule of assessments for this study is summarized in Table 4; the optional substudy assessment schedule can be found in Table 5.

 Table 4.
 Schedule of Assessments for Study BCX7353-202

	Screening  Day  -35 to -1	Baseline	Attack 1 Telephone Contacts	Post- Attack 1 Visit (10- 14 days)	Attack 2 Telephone Contacts	Post- Attack 2 Visit (10- 14 days)	Attack 3 Telephone Contacts	Post- Attack 3 Visit/ Follow-up (16 days + 3 days)	Early Termination Visit
Informed consent a	X							X	
Telephone contact b	X		X		X		X		
Clinic visits c	X	X		X		X		X	X
Inclusion/Exclusion criteria	X	X							
Medical history	X	X							
HAE attack frequency confirmation	X								
HAE medical and medication history	X								
Height/Weight/BMI	X	$X^{d}$							$X^d$
Drugs of abuse screen e	X								
HIV/HCV/HBV serology	X								
FSH f	X								
C1 INH function and C4	X								
Pregnancy test g	X	X		X		X		X	X
Safety laboratory evaluations and urinalysis testing h	X	X		X		X		X	X
Troponin I & Troponin T		X		X		X		X	X
CK-MB		X		X		X		X	X
C3		X							
C1 INH antigen level		X							

	Screening Day -35 to -1	Baseline	Attack 1 Telephone Contacts	Post- Attack 1 Visit (10- 14 days)	Attack 2 Telephone Contacts	Post- Attack 2 Visit (10- 14 days)	Attack 3 Telephone Contacts	Post- Attack 3 Visit/ Follow-up (16 days + 3 days)	Early Termination Visit
Randomization i	X								
Physical examination	X	X		$X^{j}$		$X^{j}$		$\mathbf{X}^{\mathrm{j}}$	$\mathbf{X}^{\mathrm{j}}$
$ECG^k$	X	X		X		X		X	X
Vital signs 	X	X		X		X		X	X
Diary dispensing/ instruction/review/ collection m	X	X	X	X	X	X	X	X	X
Diary completion	+								
Concomitant medications	X	X	X	X	X	X	X	X	X
AE assessment	X	X	X	X	X	X	X	X	X
Study drug dispensing/accountability and reconstitution instruction n		X		X		X		X	X
TSQM°		X		X		X		X	

a Signing of informed consent may occur in advance of the screening visit, which is defined as the visit where site-conducted screening procedures are performed. Informed consent for the observational substudy may be obtained at the follow-up visit or earlier.

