#### 10.3.4. Clinic Visits Following Study Drug Administration

Subjects will return to the clinic following the administration of study drug to treat an acute attack. Subjects will attend a total of 3 on-study clinic visits: Post-Attack 1 clinic visit, Post-Attack 2 clinic visit, and Post-Attack 3 clinic visit. After Attack 1 and Attack 2, subjects will return to the clinic 10-14 days after administration of study drug. Subjects will not be authorized to treat a subsequent attack until at least 14 days have elapsed since the last study drug administration. After Attack 3, subjects will return to the clinic for a follow-up visit 16 days after their last use of study drug (visit window permissible up to 19 days).

The following assessments will be performed at each visit:

- Targeted physical examination
- Vital signs (blood pressure, heart rate and temperature)
- 12-lead ECG (including comparison of QTcF to Baseline value)
- Review of concomitant medications and AEs
- Administration of TSQM questionnaire (TSQM will be completed in reference to the attack previously treated with study drug)
- Blood collection for clinical chemistry, hematology and coagulation
- Blood collection for CK-MB, Troponin I and Troponin T
- Urine collection for urinalysis and urine pregnancy test for female subjects of child-bearing potential
- Study drug accountability
- Post-Attack 1 and 2 clinic visits only: dispense study drug
- Collection of subject-completed HAE attack diary and review
- Post-Attack 1 and 2 clinic visits only: HAE diary dispensing for recording Attacks 2 and 3, daily HAE diaries and any applicable subject instruction sheets
- Review/re-education, as applicable, of completion of HAE attack diary, dosing instructions, phone call(s) to investigators (Post-Attack 1 and 2 clinic visits only). Subjects should record start and stop time and treatment of any additional HAE attacks that occur prior to the Post-Attack 3 visit.
- Post Attack 3 visit, for those participating in the optional observational study:

- Signing of informed consent for participation in the optional observational study (consent may be signed prior to this visit)
- Instruct and dispense diary to record details of any HAE attacks that occur

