#### 11.1.6. Clinical Laboratory Assessments

Blood and urine samples will be obtained per the schedule of events. Individual laboratory tests to be performed are provided in Table 6. Laboratory samples should be obtained in the fasted state.

Laboratory samples will be routinely analysed by a centralized laboratory with the exception of urine pregnancy tests which will be assessed locally at the site. A laboratory reference manual will be provided to the site detailing laboratory kit contents reordering instructions, sample collection, handling, storage and shipment. Results from the laboratory values should be reviewed as received by the Investigator. Evidence of this review should be provided in the source records and may include printing of the laboratory reports with a signature attesting to a review. For out-of-range lab findings, the interpretation of clinically significant or not clinically significant should be denoted in the source records. Clinically significant laboratory findings in the opinion of the Investigator should be recorded as an AE and handled as described in Section 12.1.

**Table 6.** Clinical Laboratory Evaluations

Chemistry	Hematology

 
Albumin
 
Alkaline phosphatase (ALP)
 
Alanine aminotransferase (ALT)
 
Aspartate aminotransferase (AST)
 
Bilirubin (total and direct)
 
Blood glucose (fasting)
 
Blood urea nitrogen (BUN)
 
Electrolytes (calcium, sodium, potassium, chloride, phosphorus)
 
Creatine kinase
 
	
 
Hemoglobin
 
Hematocrit
 
Erythrocytes
 
MCH
 
MCHC
 
MCV
 
White blood cell count, with differential (lymphocytes, monocytes, neutrophils, eosinophils, and basophils)
 
Platelets
 

 
Creatinine and calculated creatinine clearance
 
Gamma-glutamyltransferase (GGT)
 
Lactate dehydrogenase (LDH)
 
Total serum protein
 
Uric acid
 
Amylase
 
*reflex to lipase for amylase > 2x ULN
 
	

	Pregnancy Test			
	Serum (screening) and urine (other scheduled visits) βHCG for women of childbearing potential only			
	Drug screen			
	Amphetamines			
Urinalysis	Barbiturates			
· ·	Benzodiazepines			
Specific gravity	Cocaine			
Blood     Bilirubin	Opiates			
Glucose	Methamphetamine			
Leukocytes	• Ecstasy			
Ketones				
Nitrates	Additional Tests			
• pH	Follicle-stimulating hormone (FSH; screening)			
Protein	for women postmenopausal ≤ 2 years			

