Urobilinogen	Hepatitis B surface antigen, Hepatitis C			
Microalbumin to creatinine ratio	antibody, HIV antibody (screening)			
Microscopy if dipstick is abnormal	Troponin I Troponin T			
Coagulation	• CK-MB			
Prothrombin time (PT) and international	C1 INH function			
normalized ratio (INR)	• C4			
Activated partial thromboplastin time (aPTT)	C1 INH antigen			
· · · · · · · · · · · · · · · · · · ·	• C3			

Creatinine clearance ( $CL_{cr}$ ) will be calculated using the Cockcroft-Gault formula and actual body weight (ABW):

$$CL_{cr}$$
 (mL/min) =  $\underline{(140 - age \text{ in years}) \times ABW \text{ (kg)}}$  (× 0.85 for females)  
 $72 \times \text{serum creatinine (in mg/dL)}$ 

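### Weight is to be monitored and summarised by treatment group, but none is scheduled at any Post-Attack visit, so completers supply no post-dose weight

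*Protocol*

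**What the plan says.** Three parts of the protocol use weight after dosing or imply that it will be available.

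- Section 5.4.4.2, under presumed phospholipidosis, describes the main safeguard as a plan to "monitor organ toxicity and subject well-being through adverse event reporting and vital signs including weight".
- Section 13.3.4 lists weight among the safety variables: "Descriptive summaries of vital signs, weight, ECG parameters, and clinical laboratory results will be presented separately for each treatment group".
- Table 6 in section 11.1.6 includes "Creatinine and calculated creatinine clearance" in the chemistry panel, and the note below it says clearance "will be calculated using the Cockcroft-Gault formula and actual body weight". That panel is drawn at every Post-Attack visit.

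The schedule does not provide the measurement. In Table 4 the row "Height/Weight/BMI" is marked at Screening, Baseline and Early Termination, the last two restricted to weight by footnote d. The Post-Attack 1, 2 and 3 cells are blank. Section 10.3.4 gives the post-dose item as "Vital signs (blood pressure, heart rate and temperature" and has no separate line for weight, whereas the Early Termination list in section 10.3.5 does. The vital-signs footnote to Table 4 and section 11.1.5 do not add weight either.

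**The concern.** A safety summary by treatment group needs measurements taken after each treatment. In this crossover every completer receives two active doses and one placebo dose, so a weight is needed in each period before it can be attributed to a treatment. None is scheduled for completers. If the protocol is followed as written, the planned summary has either only pre-dose weights, which say nothing about treatment, or those plus a few weights from subjects who left early. Reasons for stopping study drug in section 8.3.2 include adverse events and laboratory abnormalities, so that group cannot stand in for the rest. The weight monitoring described in section 5.4.4.2 would not take place in anyone who completes the study.

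**Working it through.** The protocol gives no figure to reproduce. The check is a reading of the schedule, a count, and one sensitivity calculation.

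**1. Schedule.** Table 4 has nine columns: Screening, Baseline, three telephone contacts, three Post-Attack visits and Early Termination.

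- Weight: Screening, Baseline, Early Termination.
- Vital signs: those three plus Post-Attack 1, 2 and 3.
- Safety laboratories: those three plus Post-Attack 1, 2 and 3.

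The lists in sections 10.3.1, 10.3.2, 10.3.4 and 10.3.5 agree with this reading for weight, so the blank cells are not an artefact of how the table was extracted.

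**2. Scheduled post-dose weights.** Section 8.1 allows up to 36 + 12 + 12 = 60 evaluable subjects.

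- Per completer: 3 Post-Attack visits, 0 weights.
- Overall: 60 × 3 = 180 Post-Attack visits at most, 0 weights.
- Early terminators: at most one scheduled post-dose weight each, and only if a dose was taken. Each such weight follows one most recent treatment. The documents give no early-termination rate, so I put no number on this group.

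**3. If weight were added at the three visits.** Each completer would give 3 post-dose weights, 2 after active drug and 1 after placebo. With 60 completers that is 60 × 2 = 120 after active and 60 × 1 = 60 after placebo, 180 in all.

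**4. Creatinine clearance (secondary).** The Cockcroft-Gault formula in section 11.1.6 is proportional to weight. If Baseline weight is carried forward and true weight has changed by a fraction d, the relative error is 1/(1 + d) − 1. The documents give no expected weight change; these values of d are assumptions:

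- d = −10%: 1/0.90 − 1 = +11.1%
- d = −5%: 1/0.95 − 1 = +5.3%
- d = +5%: 1/1.05 − 1 = −4.8%
- d = +10%: 1/1.10 − 1 = −9.1%

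Section 10.1 anticipates participation of about 19 weeks at minimum, including screening, so a Baseline weight may be some months old by Post-Attack 3.

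**The case against.** The strongest reply is that weight is peripheral here. It is not a safety endpoint in section 7.2.2. The synopsis leaves it out of the safety criteria for evaluation and out of its own version of the summary sentence. Section 13.3.4 does not use the words post-dose or change from baseline. These points stand and hold the severity down, but they do not remove the mismatch. Screening weight is already summarised, by sequence, in section 13.3.2, so a second summary by treatment group among the on-treatment safety variables only makes sense with post-dose values. The synopsis differing from section 13.3.4 is one more inconsistency to settle.

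A reader might infer that renal safety monitoring is compromised. The documents do not support that. The kidney paragraph of section 5.4.4.2 names creatinine and urine microalbumin as the renal checks after each dose, and neither needs weight. The toxicity table in Appendix 15.1 grades creatinine, not clearance. The only clearance threshold is exclusion criterion 8, applied at Screening, where weight is measured. Specifying actual body weight says which kind of weight to use; it does not require one from the same visit.

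A reader might also infer that phospholipidosis goes unmonitored. That is too strong as well. The same paragraph considers the risk very unlikely with single doses at least 14 days apart, and relies on routine organ-safety assessments, which do take place at every Post-Attack visit.

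Finally, section 13.3 defers analysis detail to a SAP for this study. The SAP supplied is for a different trial, BCX7353-302, which schedules weight at most clinic visits, so it does not fill the gap. A SAP for this trial could drop the summary or define the weight used for clearance, but it could not create measurements that were never scheduled.

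**Conclusion.** The inconsistency is real and lies within the protocol: sections 5.4.4.2 and 13.3.4 assume weights that Table 4 and section 10.3.4 do not collect. Completers have 0 of 3 scheduled post-dose weights, and the by-treatment summary would rest, after dosing, on early terminators alone. The count of 180 visits assumes that all three parts fill to their maximum and everyone completes; the zero per completer does not depend on that. An unscheduled weight could be taken, but nothing in the protocol asks for one.

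The severity is minor. The creatinine-clearance issue is one of specification: the error of about +11% to −9% holds only for assumed weight changes of −10% to +10%, and nothing decided after dosing uses clearance.

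**What to change.** Reconcile sections 5.4.4.2, 10.3.4 and 13.3.4 with Table 4 and the synopsis. The simplest route is to add weight to the Post-Attack 1, 2 and 3 columns of Table 4 and to the section 10.3.4 list, attribute each value to the treatment taken for the preceding attack, use it in the section 13.3.4 summary, and add weight to the synopsis sentence. This costs one scale reading at visits where vital signs are already taken, plus three table cells and a line or two of text.

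If the sponsor does not want these data, remove weight from the section 13.3.4 summary and from the section 5.4.4.2 monitoring statement. That costs two edits and no data collection.

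In either case add one sentence to section 11.1.6 saying which weight enters creatinine clearance at post-dose visits: the same-visit value if it is collected, otherwise a named earlier one.

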# 13.3.5. Subject Satisfaction Analyses

The change from baseline in the TSQM global satisfaction score as well as effectiveness, side effects, and convenience subscales will be summarized. Data will be listed, summarized, and appropriately tested for differences between active treatment and placebo and between active and current acute therapy utilized at baseline.

## 13.3.6. Interim Monitoring and Statistical Stopping Rules

The study's design is intended to identify the dose or doses of BCX7353 shows an efficacy benefit over placebo. Dosing in the study will commence at the 750 mg dose level and lower doses (500 mg and 250 mg) will be evaluated in successive parts of the study.

After 12 subjects have completed Part 1 of the study, the proportion of subject attacks with a stable or improved VAS at 4 hours postdose may be estimated for BCX7353 750 mg and placebo by the study statistician using the analysis method described in Section 13.3.3. A test of no treatment difference is considered statistically significant with p < 0.001 (i.e., Haybittle-Peto boundary is crossed). Treatment differences may also be assessed using available data in Parts 1, 2 and 3 in order to plan for future studies.

